## **Randomization sequence**

The drafted randomization sequence is outlined on the MHA SMART Flow.pdf uploaded to zipline. Participants will be randomized first between a standard demographics survey to start or demographics along with a mini quiz focusing on asking a participant's primary website action intention (e.g., reading more about depression, connecting with therapists, using a DIY tool) and perceived need to do something to improve their mental health. Participants will then be randomized to types of screening results pages, with combinations of tailored responses and resources based on their responses to the demographics quiz and/or the mini quiz. For instance, if the participant chooses to continue to visit further content, they will be randomized to conditions of different presentations of a DIY question or tool on the page. Length of engagement, bounce rates, and other variables listed under metadata collection will be used to examine the impact of tailoring on engagement, which conditions and combinations of conditions result in increased engagement, and how the use of DIY tools impact engagement.

## Study 2

As previously proposed in Aim 3, we have developed an AI tool that uses machine learning / NLP / AI methods to personalize and tailor an intervention to improve engagement and completion outcomes. We focus on a specific, popular DIY tool (~10,000 users /month) that teaches cognitive restructuring. Our pilot work found that (1) engagement and completion rates on DIY tools can be low, and (2) a pilot AI tool had significantly higher engagement and completion rates. These differences may arise due to AI support, UI/UX/design differences, other factors, or a combination thereof. Additionally, the efficacy of the digital tool to improve mental health functioning is unknown. Study 2 will recruit 300 participants who will be randomly assigned to one of three groups for a longitudinal month-long study: twice-weekly DIY tool use with AI, without AI, or a control group.

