ENHANCING ENGAGEMENT WITH DIGITAL MENTAL HEALTH CARE

STUDY00010958

07/03/2024

NCT04507360

Aim 3B Statistical Analysis Plan. For Study 1, all research questions were examined via logistic regressions. We assessed whether participants' first condition (i.e., demographics survey or Next Steps survey) predicted the odds of disengagement. Within participants who completed the demographics survey, we examined whether the odds of disengaging and clicking a featured resource on the screening results page significantly differed for participants in the Tailored Resources to Demographics condition compared to control (i.e., Generic Response + Generic Resources). Within participants from the Next Steps survey condition, we tested whether engagement significantly differed for participants shown Tailored Response + Generic Resources, Generic Response + Tailored Resources to Desired Resources, and Tailored Response + Tailored Resources to Desired Resources compared to control. We aimed to identify the optimal tailoring strategy by comparing engagement across all tailoring conditions, with Tailored Resources to Demographics set as the reference group. For Study 2, research questions were examined via t-tests and Cohen's d effect sizes comparing engagement, short-term restructuring effectiveness, longer-term effectiveness (e.g., skill acquisition, reductions in depression and anxiety), and heterogeneous treatment effects by condition (i.e., control, DIY tool without AI, and DIY tool with AI).

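### Study 1 uses 9 logistic contrasts (15 if engagement means both named outcomes) to pick an optimal tailoring strategy without multiplicity control: about a 29–31% (or 38–45%) chance of a false positive if nothing works

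*SAP*

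**What the plan says.** The Aim 3B Statistical Analysis Plan is one paragraph. Its method for Study 1 is a single sentence: "For Study 1, all research questions were examined via logistic regressions". Four sets of comparisons follow.

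- **A. First survey.** "We assessed whether participants' first condition (i.e., demographics survey or Next Steps survey) predicted the odds of disengagement". One contrast, one outcome.
- **B. Demographics survey arm.** Tailored Resources to Demographics against control: "we examined whether the odds of disengaging and clicking a featured resource on the screening results page significantly differed". One contrast, two outcomes.
- **C. Next Steps survey arm.** Three tailored pages against control, with the outcome called only engagement: "we tested whether engagement significantly differed for participants shown" one of the three.
- **D. Optimal strategy.** "We aimed to identify the optimal tailoring strategy by comparing engagement across all tailoring conditions, with Tailored Resources to Demographics set as the reference group". This compares the three Next Steps tailored pages with the demographics-tailored page, again on engagement.

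The SAP does not say whether engagement in C and D means disengagement, clicks or both. It states no alpha, testing order, adjustment or primary contrast, and it labels nothing exploratory.

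The protocol does not fill the gap. Section 5.1 (Phase 3, Study 1) gives an expected 50,000 users and an optimisation goal. Under Randomization sequence it lists length of engagement, bounce rates and other metadata without ranking them, and aims to learn "which conditions and combinations of conditions result in increased engagement".

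**The concern.** Significance is the only criterion the SAP mentions. The word is attached to sets B and C, and I take it to apply to A and D as well, since no other criterion is offered. With 9 to 15 contrasts each judged alone, the chance that at least one is significant when no strategy has any effect is well above the level of a single test. Because the results are meant to name a best strategy, such an error could lead to a recommendation about which results page to use.

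The open meaning of engagement adds a second problem. If it covers both outcomes, disengagement and clicks may point to different pages, and nothing says how to settle that. If it means one outcome, the reader cannot tell which. The SAP is written in the past tense, so a deciding outcome named now could not be presented as chosen before the data were seen, unless there is a record that it was.

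**Working it through.** The documents state no error rate or power for Study 1, so there is no figure to reproduce.

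**Inputs**
- Contrasts: counted from the SAP as above.
- Alpha: not stated; two-sided 0.05 per test is assumed.
- Users: 50,000 expected (protocol section 5.1). The null error rate does not depend on this number.
- Allocation: not stated; an equal split at each randomisation is assumed. This gives 25,000 per survey, 12,500 on each of two demographics pages and 6,250 on each of four Next Steps pages.
- Correlation between disengaging and clicking: not stated; 0 to 0.8 in size is assumed. The sign is presumably negative, but with two-sided tests only the size matters.

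**Count**
- Engagement as one outcome: 1 + 2 + 3 + 3 = 9.
- Engagement as both outcomes: 1 + 2 + 6 + 6 = 15.

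**Bound if tests were independent**
- 1 − 0.95^9 = 0.370
- 1 − 0.95^15 = 0.537

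These are too high here, because contrasts share a control or reference page and the outcomes are correlated.

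**Simulation under no effects.** In 400,000 null trials (200,000 for the optimal-strategy rows), each page's estimate was drawn as normal with variance proportional to 1/n. Each contrast was z = (e_a − e_b)/√(1/n_a + 1/n_b), so shared pages carry through. The table gives the chance that at least one |z| exceeds 1.96.

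| Family | corr. 0 | 0.3 | 0.5 | 0.8 |
|---|---|---|---|---|
| All listed, 9 tests | 0.307 | 0.305 | 0.302 | 0.291 |
| All listed, 15 tests | 0.454 | 0.445 | 0.426 | 0.379 |
| Tailoring only (no set A), 8 tests | 0.287 | 0.286 | 0.282 | 0.271 |
| Tailoring only, 14 tests | 0.439 | 0.430 | 0.411 | 0.363 |
| Set D only, 6 tests | 0.251 | 0.246 | 0.235 | 0.203 |

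Set D on one outcome (3 tests) gives 0.134–0.136. With six equal pages instead, the full families give 0.285–0.303 (9 tests) and 0.373–0.446 (15 tests), so the result is not sensitive to allocation.

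**After adjustment.** Holm's first step is 0.05/k: 0.05/9 = 0.0056 and 0.05/15 = 0.0033. At those thresholds the simulated family rate is 0.038–0.044.

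**Loss of sensitivity.** Detectable difference at 80% power = (z_{1−α/2} + 0.842) × √(2 × 0.68 × 0.32/6,250). The 68% is the post-edit bounce rate in protocol section 1.8b, item 5, used as a proxy event rate. The square root is 0.834 percentage points.
- α = 0.05: (1.960 + 0.842) × 0.834 = 2.34 points
- α = 0.05/9: (2.773 + 0.842) × 0.834 = 3.02 points
- α = 0.05/15: (2.935 + 0.842) × 0.834 = 3.15 points
- α = 0.05/21 (the family proposed in the fix): (3.038 + 0.842) × 0.834 = 3.24 points

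**The case against.** The strongest objection is that these are separate research questions with planned contrasts against a named control or reference, in a website optimisation study. On that view a single family is one choice, and adjusting within each question is another. This stands as a point about how strict the control should be. It does not remove the need for some: set D alone, taken as its own family, carries about 13% on one outcome or 20–25% on two. Nor does the SAP call the work exploratory.

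Three stronger readings are tempting, and the documents do not support them.

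- **That a false tailoring claim is likely.** The chance is below one half on every reading, it is conditional on no true effects, and it rests on an assumed alpha. One counted test (set A) concerns the survey, not tailoring; without it the figures are about 27–29% or 36–44%.
- **That the two outcomes will usually crown different pages.** If all four tailored pages were equal and the best raw estimate won, the outcomes would disagree in about 35% (correlation 0.8 in size) to 75% (correlation 0) of trials. The SAP states no such rule. If a page were named only for beating the reference at 0.05, or the reference only when all three others were significantly worse, the outcomes would name different strategies in only 0.3–0.4% of null trials. That rule is an assumption too. Either way, a conflict needs engagement to mean both outcomes.
- **That disengagement should decide because the SAP mentions it more often.** Clicking is named in the same sentence for the demographics arm, and the goal in protocol section 5.1, getting users to relevant resources, fits clicks at least as well.

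**Conclusion.** The concern holds. The SAP uses 9 contrasts, or 15 if engagement covers both named outcomes, to support a claim about the optimal strategy, without multiplicity control. Assuming two-sided 0.05 per test, equal allocation at each randomisation, outcome correlation up to 0.8 in size and no true effects, the chance of at least one false positive is about 29–31% or 38–45%. That is roughly six to nine times the single-test level. A large sample does not reduce it.

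The decision rule is also incomplete. The plan gives no criterion for optimal and no rule for outcomes that disagree, and it never compares the three Next Steps tailored pages with each other. How often the outcomes would actually disagree cannot be established from the documents. The count covers only what the SAP lists; the later randomisation to DIY presentations and the further metadata outcomes in protocol section 5.1 are not in it.

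**What to change.** Add to the Study 1 SAP:

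1. Holm-adjusted p-values at two-sided 0.05 across all listed Study 1 contrasts, on both disengagement and featured-resource clicks, beside odds ratios and 95% confidence intervals. Holm is valid under any correlation between the tests.
2. Both outcomes reported for every tailoring contrast. Set A stays on disengagement, the one outcome named for it. Do not select a deciding outcome after the data; if one is named, disclose when it was chosen.
3. The three pairwise comparisons among the Next Steps tailored pages, for each outcome, in the same Holm family: 15 + 6 = 21 tests at most.
4. Wording rules. A strategy is better only than its named comparator, and only when that contrast survives adjustment. It is optimal on an outcome only if it beats every other tailored strategy after adjustment. Otherwise, state that no single optimal strategy was identified. If the outcomes disagree, report that.
5. Findings that are significant only before adjustment are labelled exploratory.

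The cost is SAP wording, a column of adjusted p-values and six further contrasts at most, with no new data. Some nominally significant results will lose that label. The detectable difference rises from about 2.3 to about 3.2 points at the strictest Holm step (3.15 for 15 tests, 3.24 for 21). Those figures assume 6,250 users per page with no losses and a proxy event rate from other pages, so the real values may be larger.

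### Study 1 sets out to find the optimal tailoring strategy, but no stated contrast separates the three tailored Next Steps pages from one another

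*SAP*

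**What the plan says.** The SAP (Aim 3B Statistical Analysis Plan, Study 1 part) fixes the method: "For Study 1, all research questions were examined via logistic regressions". It then describes three sets of page comparisons.

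- Among users given the demographics survey, the page with resources tailored to demographics is compared with the generic control page.
- Among users given the Next Steps survey, three tailored pages are each compared with control: "Tailored Response + Generic Resources, Generic Response + Tailored Resources to Desired Resources, and Tailored Response + Tailored Resources to Desired Resources compared to control". Below they are called response-only, resources-only and both-tailored.
- For the selection question, the SAP looks for the optimal strategy by "comparing engagement across all tailoring conditions, with Tailored Resources to Demographics set as the reference group".

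The SAP states no contrast between two tailored Next Steps pages. It also states no overall test, change of reference, ranking rule, simultaneous interval or multiplicity rule for Study 1.

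The protocol (section 5.1, Randomization sequence) says that users are "randomized first between a standard demographics survey to start or demographics along with a mini quiz", and only afterwards randomised to a results page. It wants to learn "which conditions and combinations of conditions result in increased engagement", and it adds no comparison that the SAP lacks.

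**The concern.** The selection step asks a which-is-best question, but its stated contrasts answer a different one: does each Next Steps page differ from the demographics-tailored page? If two or three Next Steps pages beat that reference, no stated test chooses among them. If only some reach significance, a reader will be tempted to rank them on that pattern. The trial could then name an optimal page without having tested it against its closest rivals.

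The omitted pairs are also the cleanest ones. The reference page belongs to the demographics-survey arm, and the three Next Steps pages belong to the arm that also received the mini quiz. Each contrast in the selection step therefore mixes the effect of the page with the effect of the survey that came before it. The SAP treats the survey as a possible influence in its own right, because it tests whether the first condition predicts disengagement. Two Next Steps pages compared with each other share the same survey, so that mixing does not arise.

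**Working it through.** **Step 1. Count the contrasts (from the SAP).** There are four tailored pages: one in the demographics arm and three in the Next Steps arm. Pairs: 4 × 3 / 2 = 6. A single reference group gives 4 − 1 = 3 contrasts. The three missing pairs are response-only v resources-only, response-only v both-tailored, and resources-only v both-tailored. The page-versus-control step supplies none of them.

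**Step 2. Assumptions for an illustration.** The documents give an expected 50,000 users for Study 1 but no engagement rate, effect size, alpha or allocation ratio, so there is no stated figure to reproduce. Assumed:

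- All 50,000 reach a results page.
- Even splits at each stage: 25,000 per survey arm; 25,000 / 2 = 12,500 on each of two demographics-arm pages; 25,000 / 4 = 6,250 on each of four Next Steps pages.
- Engagement on the reference page is 30%, and tests are two-sided at 0.05.

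**Step 3. Precision.**

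- Next Steps page v reference: SE = √[0.3 × 0.7 × (1/12,500 + 1/6,250)] = 0.71 points, so an observed difference of about 1.96 × 0.71 = 1.4 points reaches significance.
- Next Steps page v Next Steps page: SE = √(2 × 0.3 × 0.7 / 6,250) = 0.82 points, a 95% half-width of about 1.6 points.

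**Step 4. How often the reference tests split identical pages.** Three Next Steps pages share the same true rate, and 200,000 trials are simulated. A split means that one or two of the three, but not all three, are significant against the reference.

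| True advantage over reference (points) | Split |
|---|---|
| +0 | 13% |
| +0.5 | 25% |
| +1.0 | 49% |
| +1.5 | 58% |
| +2.0 | 40% |
| +2.5 | 16% |
| +3.0 | 4% |
| +4.0 | about 0% |

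At +1.5 points the chances of 0, 1, 2 or 3 significant results are 0.16, 0.27, 0.31 and 0.25, and 0.27 + 0.31 = 0.58. The peak lies there because 1.5 points is close to the 1.4-point threshold from step 3.

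Other allocations change the height or place of the peak. At +1.5 points the split is 49–50% with 8,333 users on every page, and 52% if only half the users reach the page (6,250 and 3,125). From a 10% reference rate, advantages of +1.0, +1.5 and +2.0 points give 58%, 27% and 4% at full size, and 52%, 57% and 34% at half size.

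**Step 5. When all three beat the reference.** Take constructed counts of 1,250/12,500 on the reference (10%) and 750, 812 and 875 out of 6,250 (about 12, 13 and 14%). The odds ratios against the reference are 1.227, 1.344 and 1.465, each with p < 0.0001. The stated tests stop there. The missing contrasts follow from the same fit:

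- 1.344 / 1.227 = 1.095 (p = 0.094)
- 1.465 / 1.344 = 1.090 (p = 0.099)
- 1.465 / 1.227 = 1.194 (p = 0.0009)

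These p-values are unadjusted. The top page is separated from the third page but not from the second, and the three reference contrasts do not show this.

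**Step 6. What the added contrasts could detect.** With Bonferroni 0.05/3 for the three head-to-heads and 80% power, the smallest detectable difference is about 1.8 points from a 10% base (1.6 to 2.6 over the allocations above) and 2.7 points from a 30% base (2.3 to 3.8).

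**The case against.** The SAP is a one-paragraph summary, and naming a reference group may only describe how a categorical predictor was coded, not list every contrast to be reported. A reader might infer that the Next Steps pages can never be compared, or that the plan can never say which page is best. The documents do not support either reading. Each missing pair is a difference of two coefficients in the model already named. Odds ratios against a common reference give a descriptive order of all four pages. If the demographics-tailored page beat the other three, the stated contrasts could identify it as best. Comparison across all conditions might even be meant to include an overall test, although none is stated and it would not say which page leads.

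The simulated figures also need restraint. Quoting 58% alone would overstate the problem, because it sits near the top of a range that runs from about 0%.

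Nor would better contrasts always yield a winner. With true rates of 32.5, 33.0 and 33.5% against 30%, all three pages beat the reference in 92% of trials, and the page with the highest observed rate is truly best in 67%. That 67% reflects half-point gaps against a 0.82-point SE, not the choice of reference. A Tukey-type rule would separate the leading page from the runner-up in only about 1% of those trials. With wider gaps (32, 34 and 36%), simple ranking finds the best page 99% of the time. Choosing the highest observed page is a defensible practical decision for low-risk web content.

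All of this stands. It limits the point to a missing contrast and decision rule. It does not supply either.

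**Conclusion.** The point holds in this form: the stated goal is to identify the optimal strategy, the stated contrasts cover three of the six pairs, and no stated test, interval or rule separates the three tailored Next Steps pages. That follows from the SAP text alone and depends on no assumed number. The size of the risk does depend on assumptions. With a 30% reference rate and the even-split allocation, identical pages are spuriously split in anything from about 0% to 58% of trials, with the worst case where the true advantage is close to the detection threshold. The consequence is a possible unsupported claim about which page is best. No data are lost and the randomisation is unaffected, so this is a modest correction, worth making before any page is called optimal.

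**What to change.** From the same logistic model, add the three Next Steps head-to-head contrasts, so that all six pairs of tailored pages are reported with multiplicity-adjusted intervals (Tukey-type, for example). Describe a page as shown to be best only where those contrasts support it. Otherwise report the highest-ranked page as a descriptive choice, together with the pages not distinguishable from it. Say also that the three contrasts with the demographics-tailored page compare survey and page together.

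The cost is a contrast statement on a model already specified, with no new data. The downside is wider intervals. For four groups the Tukey critical value is about 2.57 in place of 1.96, so the head-to-head half-width under the assumptions above goes from 1.6 to about 2.57 × 0.82 = 2.1 points. If the true differences are small, the answer will often be a set of pages rather than one winner.
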